#### 11.5 Serious and non-serious Adverse Event Reporting

In the event of an **SAE**, the physician will:

- For events from patients using the ABBVIE REGIMEN ± RBV (or any other AbbVie authorized product) report to AbbVie within 24 hours of the physician becoming aware of the event by using the eCRF system or notifying the AbbVie contact person identified in Section 11.0.
- For events from patients using a non-AbbVie product - notify the Marketing Authorization Holder (MAH) of the product within 24 hours of the physician becoming aware of the event.

In the event of a **non-serious AE**, the physician will:

- For events from patients using the ABBVIE REGIMEN ± RBV report to AbbVie by using the eCRF system.

#### 11.6 Pregnancy Reporting

Patients and their partners should avoid pregnancy and males should avoid sperm donation throughout the course of the HCV treatment and for 30 days after the end of treatment with DAAs only, or for 7 months after the last dose of RBV (or per local RBV label) and/or consistent with local treatment guidelines for RBV.

In the event of a pregnancy occurrence in the patient, the physician will report to AbbVie within 24 hours of the physician becoming aware of the pregnancy by using the eCRF system or notifying the AbbVie contact person identified in Section 11.0.

---

Confidential Information

The investigator is encouraged to report the pregnancy information to the voluntary RBV Pregnancy Registry, if RBV is included within the regimen.

## **12.0 Plans for Disseminating and Communicating Study Results**

At the end of this observational study, a report will be written by AbbVie or a CRO working on behalf of AbbVie. The required standard study report template will be followed. This report will contain a description of the objectives of the study, the methodology and its results and conclusions. The completed eCRFs, [patient questionnaires, interim assessments] the final study output and study report are the confidential property of AbbVie and may not be released to unauthorized people in any form (publications or presentations) without express written approval from AbbVie. The study results will be submitted to local authorities by the participating countries per local laws and regulations.

The results of this study will be made publicly available on one of the primary registries in the World Health Organization (WHO) Registry Network which meet the requirements of the International Committee of Medical Journal Editors (ICMJE) and through scientific publications. Authorship will be in line with ICMJE' authorship requirements [76].

**Confidential Information**

## Annex 1. FACIT-F - The Functional Assessment of Chronic Illness Therapy-Fatigue Scale

Below is a list of statements that other people with your illness have said are important. Please circle or mark one number per line to indicate your response as it applies to the past 7 days.

		Not at all	A little bit	Some-what	Quite a bit	Very much
HI7	I feel fatigued.....	0	1	2	3	4
HI12	I feel weak all over.....	0	1	2	3	4
An1	I feel listless ("washed out").....	0	1	2	3	4
An2	I feel tired.....	0	1	2	3	4
An3	I have trouble starting things because I am tired.....	0	1	2	3	4
An4	I have trouble finishing things because I am tired.....	0	1	2	3	4
An5	I have energy.....	0	1	2	3	4
An7	I am able to do my usual activities.....	0	1	2	3	4
An8	I need to sleep during the day.....	0	1	2	3	4
An12	I am too tired to eat.....	0	1	2	3	4
An14	I need help doing my usual activities.....	0	1	2	3	4
An15	I am frustrated by being too tired to do the things I want to do.....	0	1	2	3	4
An16	I have to limit my social activity because I am tired.....	0	1	2	3	4

**Confidential Information**

## Annex 2. Work Productivity and Activity Impairment (WPAI)

### Work Productivity and Activity Impairment Questionnaire Hepatitis C, V2 (WPAI: Hepatitis C)

The following questions ask about the effect of your hepatitis C on your ability to work and perform normal daily activities. Please fill in the blanks or circle a number, as indicated.

- 1) Are you currently in paid employment?  NO  YES  
If NO, tick "NO" and skip to question 6.

The next questions refer to the **past seven days**, not including today.

- 2) During the past seven days, how many hours did you miss from work because of problems associated with your hepatitis C? Include hours you missed on sick days, times you went in late, left early, etc., because of your hepatitis C. Do not include time you missed to participate in this study.

\_\_\_\_\_ HOURS

- 3) During the past seven days, how many hours did you miss from work because of any other reason, such as annual leave, holidays, time off to participate in this study?

\_\_\_\_\_ HOURS

- 4) During the past seven days, how many hours did you actually work?

\_\_\_\_\_ HOURS (If "0", skip to question 6.)

---

Confidential Information

5. During the past seven days, how much did hepatitis C affect your productivity while you were working?

*Think about days you were limited in the amount or kind of work you could do, days you accomplished less than you would like, or days you could not do your work as carefully as usual. If hepatitis C affected your work only a little, choose a low number. Choose a high number if hepatitis C affected your work a great deal.*

Consider only how much hepatitis C affected productivity while you were working.

Hepatitis C had no effect on my work	_____	Hepatitis C completely prevented me from working
	0 1 2 3 4 5 6 7 8 9 10	

CIRCLE A NUMBER

6. During the past seven days, how much did your hepatitis C affect your ability to perform your normal daily activities, excluding your job?

*By normal activities, we mean the usual activities you perform, such as working around the house, shopping, childcare, exercising, studying, etc. Think about times you were limited in the amount or kind of activities you could perform and times you accomplished less than you would like. If hepatitis C affected your activities only a little, choose a low number. Choose a high number if hepatitis C affected your activities a great deal.*

Consider only how much hepatitis C affected your ability to perform your normal daily activities, excluding your job.

Hepatitis C had no effect on my daily activities	_____	Hepatitis C completely prevented me from performing my daily activities
	0 1 2 3 4 5 6 7 8 9 10	

CIRCLE A NUMBER

WPAI: HepC V2.0 (English - United Kingdom)

In Germany the German Version WPAI: HepC V2.1 (German - Germany) will be used

---

### Annex 3. Pictorial Representation of Illness and Self-Measure (PRISM)

#### PRISM-Instrument

The examiner presents a white, A-4 sized paperboard with a fixed yellow circle in the lower right corner, measuring 7cm in diameter. He explains to the patient that the plate represents his life and that the yellow circle represents the centre of his life, his “self”. Then he introduces a red magnetic disc having a diameter of 5cm as “illness”

#### Conducting the PRISM-test and measurement of self-illness-separation (SIS)

The examiner asks the patient to place the red disc on the board in such a way that it shows which place the illness currently occupies in his life. The distance between the centre of the “self” and the illness disc is called “self-illness separation” SIS and is measured in cm. The minimum amounts to 0cm, the maximum to 27cm (range is 0-27)

## Annex 4. PAM-13 Questionnaire Sample

Below are some statements that people sometimes make when they talk about their health. Please indicate how much you agree or disagree with each statement as it applies to you personally by circling your answer. Your answers should be what is true for you and not what you think others might want you to say.

If the statement does not apply to you, circle N/A.

1. When all is said and done, I am the person who is responsible for taking care of my health	Disagree Strongly (1)	Disagree (2)	Agree (3)	Agree Strongly (4)	N/A (5)
2. Taking an active role in my own health care is the most important thing that affects my health	Disagree Strongly (1)	Disagree (2)	Agree (3)	Agree Strongly (4)	N/A (5)
3. I am confident I can help prevent or reduce problems associated with my health	Disagree Strongly (1)	Disagree (2)	Agree (3)	Agree Strongly (4)	N/A (5)
4. I know what each of my prescribed medications do	Disagree Strongly (1)	Disagree (2)	Agree (3)	Agree Strongly (4)	N/A (5)
5. I am confident that I can tell whether I need to go to the doctor or whether I can take care of a health problem myself	Disagree Strongly (1)	Disagree (2)	Agree (3)	Agree Strongly (4)	N/A (5)
6. I am confident that I can tell a doctor concerns I have even when he or she does not ask	Disagree Strongly (1)	Disagree (2)	Agree (3)	Agree Strongly (4)	N/A (5)
7. I am confident that I can follow through on medical treatments I may need to do at home	Disagree Strongly (1)	Disagree (2)	Agree (3)	Agree Strongly (4)	N/A (5)
8. I understand my health problems and what causes them	Disagree Strongly (1)	Disagree (2)	Agree (3)	Agree Strongly (4)	N/A (5)
9. I know what treatments are available for my health problems	Disagree Strongly (1)	Disagree (2)	Agree (3)	Agree Strongly (4)	N/A (5)
10. I have been able to maintain (keep up with) lifestyle changes, like eating right or exercising	Disagree Strongly (1)	Disagree (2)	Agree (3)	Agree Strongly (4)	N/A (5)
11. I know how to prevent problems with my health	Disagree Strongly (1)	Disagree (2)	Agree (3)	Agree Strongly (4)	N/A (5)
12. I am confident I can figure out solutions when new problems arise with my health	Disagree Strongly (1)	Disagree (2)	Agree (3)	Agree Strongly (4)	N/A (5)
13. I am confident that I can maintain lifestyle changes, like eating right and exercising, even during times of stress	Disagree Strongly (1)	Disagree (2)	Agree (3)	Agree Strongly (4)	N/A (5)

Insignia Health. "Patient Activation Measure; Copyright © 2003–2011, University of Oregon. All Rights reserved." Contact Insignia Health at [www.insigniahealth.com](http://www.insigniahealth.com)

DRAFT Version 0.03/CBA BG

## Annex 5. Patient Support Program (PSP) Utilization Questionnaire

### Patient Support Program (PSP) Utilization Questionnaire

12 weeks treatment: At Interim early post-treatment visit

24 weeks treatment: At Interim mid treatment visit and Interim early post-treatment visit

Since the last visit, have you utilized any components from the AbbVie Patient Support Program?

No

→ Please ignore questions below and return questionnaire to your physician or study nurse

Yes

↓  
Please specify service(s) used:

●  Personal support (e.g. Care Coach)

▲  Educational and information material (e.g. magazines, leaflets, diaries)

✘  Printed

→ Please specify how often used:  Usually daily  
 Several times per week  
 Usually once weekly  
 Less than once weekly

✚  Online

→ Please specify how often used:  Usually daily  
 Several times per week  
 Usually once weekly  
 Less than once weekly

■  Additional digital and mobile resources

★  Web-portal

→ Please specify how often used:  Usually daily  
 Several times per week  
 Usually once weekly  
 Less than once weekly

●  Reminders

## Annex 6. Patient Support Program (PSP) Utilization and Satisfaction Questionnaire

### Patient Support Program (PSP) Utilization and Satisfaction Questionnaire

12 weeks treatment: At Interim early on-treatment visit, week 12 EoT visit and SVR 12 visit

24 weeks treatment: At Interim early on-treatment visit, week 24 EoT visit and SVR 12 visit

Since the last visit, have you utilized any components from the AbbVie Patient Support Program?

No

→ Please ignore questions below and return questionnaire to your physician or study nurse

Yes

→ What is your level of satisfaction of the AbbVie Patient Support Program in general?

- Very good
- Good
- Satisfactory
- Poor

→ Did the Program address your needs?  Yes, fully  Yes, mostly  No

Please specify service(s) used:

●  Personal support (e.g. Care Coach)

→ Please specify your level of satisfaction:  Very good  
 Good  
 Satisfactory  
 Poor

▲  Educational and information material (e.g. magazines, leaflets, diaries)

✘  Printed

→ Please specify how often used:  Usually daily  
 Several times per week  
 Usually once weekly  
 Less than once weekly

→ Please specify your level of satisfaction:  Very good  
 Good  
 Satisfactory  
 Poor

✚  Online

→ Please specify how often used:  Usually daily  
 Several times per week  
 Usually once weekly  
 Less than once weekly

→ Please specify your level of satisfaction:  Very good  
 Good  
 Satisfactory  
 Poor

### Confidential Information

No use or disclose outside AbbVie is permitted without prior written authorization from AbbVie

■  Additional digital and mobile resources

- ★  Web-portal
- Please specify how often used:  Usually daily  
 Several times per week  
 Usually once weekly  
 Less than once weekly
  - Please specify your level of satisfaction:  Very good  
 Good  
 Satisfactory  
 Poor

- Reminders
- Please specify your level of satisfaction:  Very good  
 Good  
 Satisfactory  
 Poor

---

[figure not shown]

## GLOSSARY OF ABBREVIATIONS

AE	adverse event
APRI	AST to platelet ratio index
AFP	alfa fetoprotein
ALT	alanine-aminotransferase
AST	aspartate-aminotransferase
ANCOVA	analysis of covariance
BMI	body mass index
BMQ	beliefs medication questionnaire
CA	competent authority
CD4	cluster of differentiation 4
CHC	chronic hepatitis C
CI	confidence interval
CNI	calcineurin
CP	core population
CPFSU	core population with sufficient follow-up data
CT	computer tomography
DAA	direct-acting antiviral agent
DDI	drug-drug interaction
EC	ethics committee
EDC	electronic data capture
eCRF	electronic case report form
EMA	European Medicines Agency
EoT	end of treatment
EQ-5D-5L	EuroQol 5 dimension 5 level
FACIT-Fatigue	Functional Assessment of Chronic Illness Therapy-Fatigue
FDA	Food and Drug Administration
FIB-4	Fibrosis-4 Score/Index
γ-GT	gamma-glutamyltransferase
HCC	hepatocellular carcinoma
HCP	health care provider
Hb	hemoglobin
HbA1c	hemoglobin A1c

## GLOSSARY OF ABBREVIATIONS

HBV	hepatitis B virus
HCV	hepatitis C virus
HDL	high-density lipoprotein
HIV	human immunodeficiency virus
HOMA	homeostasis model assessment
HVPG	hepatic venous pressure gradient
ICMJE	International Committee of Medical Journal Editors
IEC/IRB	independent ethics committee/- review board
IgA	Immunoglobulin A
IgG	Immunoglobulin G
IgM	Immunoglobulin M
INN	international non-proprietary name
INR	international normalized ratio
LDL	low-density lipoprotein
LLoD	lower limit of detection
LLoQ	lower limit of quantification
MAH	Marketing Authorization Holder
MedDRA	Medical Dictionary for Regulatory Activities
MLR	multiple logistic regression
MRI	magnetic resonance imaging
NCP	non-core population
NS3/NS4A	nonstructural protein 3/nonstructural protein 4A
NS5A	nonstructural protein 5A
NS5B	nonstructural protein 5B
OATP	organic anion-transporting polypeptide
OLT	orthotopic liver transplant
PAM-13	Patient Activation Measure 13
paritaprevir/r	paritaprevir/ritonavir
PCR	polymerase chain reaction
pegIFN	pegylated interferon
PRISM	Pictorial Representation of Illness and Self-Measure
PRO	patient reported outcome
PT	preferred term

## GLOSSARY OF ABBREVIATIONS

RBV	ribavirin
RF	rheumatoid factor
RNA	ribonucleic acid
SAE	serious adverse event
SAP	statistical analysis plan
SD	standard deviation
SDP	study designated physician
SNP	single nucleotide polymorphism
SOC	system organ class
SP	safety population
SVR	sustained virological response
SVR12	SVR at 12 weeks after EoT
SVR24	SVR at 24 weeks after EoT
SVR48	SVR at 48 weeks after EoT
TAI	total activity impairment
TP	target population
TWP	total work productivity impairment
VAS	visual analogue scale
WHO	World Health Organization
WPAI	work productivity and activity impairment
WPAI-GH	WPAI as general health measure
WPAI-SHP	WPAI modified for specific health condition

## 1 Introduction

The interferon-free combination regimen of paritaprevir/r and ombitasvir with or without dasabuvir (ABBVIE REGIMEN) ± ribavirin (RBV) for the treatment of chronic hepatitis C (CHC) has been shown to be safe and effective in randomized controlled clinical trials with strict inclusion and exclusion criteria under well controlled conditions.

The rationale for this observational study is to determine how the efficacy and safety of the ABBVIE REGIMEN as demonstrated in pivotal trials translates into real world everyday clinical settings, which means evaluating its effectiveness. Whereas efficacy can be defined as a measure of the capacity of a treatment to produce the desired effect in a controlled environment, such as in a randomized controlled trial, effectiveness is the extent to which a drug achieves its intended effect in the usual clinical setting. Effectiveness trials typically have limited exclusion criteria and will involve the broader patient populations in routine clinical practice, treated per local label, which might include patients with heterogeneous compliance patterns and patients with significant comorbid conditions and could be used to model and disseminate best practices. Effectiveness research allows for external patient-, provider-, and system-level factors and can therefore be more relevant for health-care decisions by both providers in practice and policy-makers.

This observational study is the first effectiveness research examining the ABBVIE REGIMEN ± RBV, used according to local label, under real world conditions in Germany in a clinical practice patient population.

During the last decade, when dual therapy with pegylated interferon (pegIFN) plus RBV was standard of care for the treatment of CHC, the discovery of predictive factors for virological response and the subsequent development of treatment algorithms marked a milestone in patient care for CHC. As a consequence, treatment could be effectively targeted to patients most likely to respond. Interestingly, many of the now well established predictors of response to pegIFN/RBV and first generation direct acting antivirals (DAAs) in combination with pegIFN/RBV were not predictive of outcome in the development trials of the ABBVIE REGIMEN ± RBV. This observational study may play an important part in bridging the data gaps. It may help identify predictive factors of response that are important in real world treatment settings and thus, could assist in further optimizing treatment with the interferon-free ABBVIE REGIMEN ± RBV in the future.

The label of the ABBVIE REGIMEN ± RBV will vary according to hepatitis C virus (HCV) genotype/subtype and stage of liver disease. It is therefore relevant to understand the pattern of use and outcome in daily clinical practice. In addition, this study will provide data on the impact of adherence on treatment outcomes in everyday settings, which may help treating physicians to improve the management of patients under their care.

The main aim of this observational study is to provide evidence of the effectiveness of the ABBVIE REGIMEN ± RBV in a real world setting across clinical practice patient populations.

## 2 Study Objectives

The objectives of this study are:

***Primary objective:***

1. To describe in routine clinical practice the effectiveness of the interferon-free ABBVIE REGIMEN ± RBV in patients with CHC as evidenced by sustained virological response at 12 weeks after end of treatment (SVR12)

***Secondary objectives:***

2. To provide real world evidence for predictive factors of virological response
3. To describe the pattern of real world use of the ABBVIE REGIMEN ± RBV with respect to different patient and treatment characteristics
4. To evaluate the influence of adherence on treatment outcome in routine clinical practice
5. To collect information on co-morbidities and concomitant medication in the German population
6. To describe the tolerability of the ABBVIE REGIMEN ± RBV
7. To document the effect of the ABBVIE REGIMEN ± RBV on PROs and work productivity in the German population

## 3 Study Design

### 3.1 Overview of Study Design and Dosing Regimen

This is a prospective, multi-center observational study in adult patients chronically infected with HCV receiving the interferon-free ABBVIE REGIMEN ± RBV.

University centers and outpatient clinics qualified by training and experience in the management of patients with CHC participate in this study.

The prescription of a treatment regimen is at the discretion of the physician in accordance with local clinical practice and label, is made independently from this observational study and precedes the decision to offer the patient the opportunity to participate in this study.

After written patient authorization has been obtained, patient data including demographic data, HCV disease characteristics, co-morbidities, co-medication, treatment details, and laboratory assessments as recorded in the patient's medical records (source documentation) are documented in the electronic case report form (eCRF). Patients are observed for the duration of the ABBVIE REGIMEN therapy and for up to 48 weeks after treatment completion.

[figure not shown]
The observational period for patients receiving 12 weeks of ABBVIE REGIMEN is max. 60 weeks (12 weeks treatment and 48 weeks post-treatment observation) and for patients receiving 24 weeks of ABBVIE REGIMEN the observational period is max. 72 weeks (24 weeks treatment and 48 weeks post-treatment observation).

Follow-up visits, treatment, procedures and diagnostic methods follow physicians' routine clinical practice. The observational study period entails the following data collection schemes, data documented are those closest to the time windows as indicated in Figure 1:

- 12-week treatment regimen: five visits plus two interim data collection windows
- 24-week treatment regimen: five visits plus three interim data collection windows

This schedule is based on the anticipated regular follow-up for patients undergoing treatment for CHC.

**Figure 1 - Study Flowchart**

### 3.2 Sample Size Calculation

In studies investigating the interferon-free ABBVIE REGIMEN  $\pm$  RBV, SVR12 rates of about 95% were observed, even in difficult-to-treat CHC patients (e.g. cirrhotic G1a treatment experienced patients). To describe in routine clinical practice the effectiveness of the ABBVIE REGIMEN  $\pm$  RBV in patients with CHC a precise estimate of the SVR12 rates in the core population of this study should be achieved (see Section 4.2.1 for the definition of the core population).

It is expected, that during the planned recruitment period of 12 months about 650 patients with ABBVIE REGIMEN  $\pm$  RBV can be included into this observational study, and that at least 620 patients will be evaluable in the core population. As obvious from Table 1, if the SVR12 rate is at least 95%, then with 620 patients the width of the 95% confidence interval (CI) will not be wider than 3.5%. Even in the case that fewer patients will be enrolled and only 590 patients can be evaluated in the core population, the 95% CI will have a width of  $\leq 3.6\%$  for a SVR12 rate of 95%.

**Table 1** Width of 95% Confidence Interval for SVR12

Number of patients	SVR12 rates	95% Confidence Interval*			Width
		Lower Limit	Upper Limit		
620	95%	93.0	96.5	3.5%	
590	95%	92.9	96.5	3.6%	
62	95%	86.5	98.3	11.8%	

\* exact two-sided 95% confidence interval according to Wilson's Score method

Assuming, that in total 620 patients will be evaluable, and subgroups of interest consist of at least 10% of the entire group (i.e.  $\geq 62$  patients), then the width of the 95% CI will be  $< 12\%$  for a SVR12 rate of 95%, which is also considered sufficiently precise for subgroup analyses.

## 4 Statistical Considerations and Analytical Plan

### 4.1 Primary and Secondary Parameters

#### 4.1.1 Primary Effectiveness Parameter

The percentage of patients achieving SVR12 (HCV RNA  $< 50$  IU/mL 12 weeks [i.e. 70 to 126 days] after the last actual dose of the ABBVIE REGIMEN).

Please note, in the study protocol no upper boundary for the time window was specified. The upper boundary of 126 days was introduced to achieve consistency with other studies investigating the ABBVIE REGIMEN  $\pm$  ribavirin (RBV) for the treatment of CHC. For the handling of missing values see section 4.2.3.

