## 9.3 Variables

### 9.3.1 Primary Variable

- The percentage of patients achieving SVR12 (HCV RNA <50 IU/mL 12 weeks [i.e. ≥70 days] after the last actual dose of the ABBVIE REGIMEN)

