No data will be imputed for any effectiveness or safety analyses except for the analyses of the HCV RNA endpoints. When there is no HCV RNA value in a visit time window post-baseline, but prior to EoT, the closest values before and after the window, regardless of the value chosen for the subsequent and preceding window, will be used for the flanking imputation described below. If a patient has a missing HCV RNA value at a post-baseline visit prior to EoT but has undetectable HCV RNA (with LLoD  $\leq 50$  IU/mL) or unquantifiable, but detectable HCV RNA levels (with LLoQ  $\leq 50$  IU/mL) at both the preceding and succeeding measurements, the HCV RNA level will be considered undetectable or unquantifiable, respectively, at this visit for this patient. In addition, if a patient has an unquantifiable HCV RNA level at the preceding measurement and an undetectable HCV RNA level at the succeeding measurement, or vice versa, the HCV RNA level will be imputed as unquantifiable at this visit for this patient. For virological response at EoT a corresponding backward imputation approach will be applied. This means if HCV RNA is missing at EoT, then unquantifiable or undetectable will be assumed for EoT, if the succeeding HCV RNA value is undetectable or unquantifiable. For SVR12 the single last available HCV RNA measurement  $\geq 70$  days post-treatment will be used. Subsequent to this flanking and backward imputation, if the HCV RNA value remains missing at a specific time point, then the patients will be considered as virological failure at this time point (i.e. not undetectable or unquantifiable).

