#### 9.7.3.1 Primary Effectiveness Endpoint

The percentage of patients achieving SVR12 (single last HCV RNA  $< 50$  IU/mL 12 weeks [i.e. at least 70 days] after the last actual dose of the ABBVIE REGIMEN) is the primary effectiveness endpoint.

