#### 4.2.9.4 Fourth Interim Analysis

A fourth IA was performed in August 2017 (data snapshot: 21 August 2017).

Site information and researcher experience were displayed, as well as patient disposition by genotype and cirrhosis status for the EP.

The following tables were created for the CP:

- treatment regimen
- premature termination of treatment and its main reason
- socio-demographic characteristics
- CHC disease characteristics
- CHC Related laboratory variables at baseline
- other key laboratory variables at baseline
- CHC treatment history in treatment experienced patients
- Co-morbidities and co-infections
- alcohol consumption
- CD4 and HIV-RNA in patients with HIV at baseline
- Adherence
- Virological response rates (once in all patients and once in patients who completed AbbVie regimen)
- Relapse rates
- Viral breakthrough
- PRISM, FACIT Fatigue Subscale Score (not normed), WPAI, PAM13 over time (including pre-post comparisons)

Non-response rates were displayed for the CPSFU12 (once in all patients and once in patients who completed AbbVie regimen). All tables were structured by genotype and cirrhosis status, except for the analyses regarding questionnaires. These analyses were structured by treatment regimen and cirrhosis status. The analyses were repeated replacing cirrhosis status once by age ( $\geq 70/ < 70$  years) and once by opiate substitution (no/ yes; yes, is defined as patients with psychoactive substance dependency - opiate substitution).

Furthermore ANOVAs were conducted in addition to descriptive statistics (i.e. mean, median, SD, SE, 95%CI of the mean) to describe the association between disease characteristics and SIS (PRISM) for categorial variables. The following disease characteristics were considered: sex, age (18-69 years,  $\geq 70$  years), race / ethnic origin (White/Caucasian, Asian/Oriental), BMI [kg/sqm] ( $<25$ ,  $25-30$ ,  $\geq 30$ ), HCV genotype (G1/G4), HCV RNA [IU/mL] ( $800,000, \geq 800,000$ ), mode of HCV infection (drug use [i.v./non i.v.], blood transfusion or transplantation, unknown, sexual transmission, blood transfusion or transplantation, other [all other modes]), years since diagnosis of HCV infection ( $\leq 5$ ,  $6-10$ ,  $11-15$ ,  $\geq 16$ ), cirrhosis status at BL (yes/no), HCV Co-infection, liver and/or CHC related co-morbidities, other co-morbidities, opiate substitution. (For co-morbidities

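### The SAP's 70–126 day window drops the protocol's last-value rule for SVR12, and no planned output gives the protocol-defined rate in the core population

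*SAP*

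**What the plan says.** Protocol 9.3.1 sets the primary variable as "HCV RNA <50 IU/mL 12 weeks [i.e. ≥70 days] after the last actual dose of the ABBVIE REGIMEN", with no upper limit. Protocol 9.7.3.1 ties the endpoint to one value, the "single last HCV RNA" result in that period. Protocol 9.7.1 repeats this: "For SVR12 the single last available HCV RNA measurement" from day 70 onward is the one used. Section 9.7.1 also leaves the HCV RNA visit windows to the SAP, although it names the value that decides SVR12 itself.

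SAP 4.1.1 requires HCV RNA below 50 "IU/mL 12 weeks [i.e. 70 to 126 days] after the last actual dose of the ABBVIE REGIMEN". It notes that "in the study protocol no upper boundary for the time window was specified" and gives the reason: "The upper boundary of 126 days was introduced to achieve consistency with other studies". SAP Table 3 repeats the window and assigns days 127–210 to SVR24 and later days to SVR48.

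Under SAP 4.2.3, an empty window is filled first by flanking imputation and then, if still empty, from a value after it. The same section discards values from the start of any new HCV treatment and counts the patient as a failure from then on. The protocol has no such rule.

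SAP 4.2.7.1 repeats the primary analysis in the CPSFU as a sensitivity analysis and adds the NCP rate. SAP Table 8 lists no output under another SVR12 rule. SAP 4.2.7.2.1 adds relapse by window, SVR24 and SVR48.

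**The concern.** The primary endpoint is computed by a different rule in the SAP than in the protocol, and the disclosure covers only half of the change. The SAP reports the added upper limit. It does not say that the last value no longer decides, nor which value counts when several fall between days 70 and 126.

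Both planned variations, CPSFU and NCP, change the population and keep the endpoint rule. A reader who compares the report with the protocol cannot tell whether the headline rate depends on the definition.

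The SAP rule also makes the result depend on when a patient happened to be tested, which is left to the physician. Take two patients with the same late relapse. One had a negative test in the window and counts as a success. The other had no test in the window, and the first later value is 50 IU/mL or more; that patient counts as a failure. Under the protocol rule both are failures.

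**Working it through.** **Where the rules agree and differ (leaving retreatment aside)**

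| HCV RNA values from day 70 onward | Protocol | SAP |
|---|---|---|
| None | failure | failure |
| Exactly one, at any time | that value decides | that value decides (in window, or imputed into it) |
| In window <50, last value after day 126 ≥50 | failure | success |
| In window ≥50, last value after day 126 <50 | success | failure |
| Several in window that disagree, none later | last one decides | not stated |
| Window empty, several later values that disagree | last one decides | window filled by flanking or backward imputation |

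The rules can therefore differ only for patients with repeat values that disagree. The retreatment rule is a further difference: a failure who starts new HCV treatment and is later below 50 is a SAP failure but, as the protocol is written, a protocol success.

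**The plan's own precision figure**

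Inputs from SAP 3.2 and Protocol 9.5: n = 620, p = 0.95, Wilson score, z = 1.96.

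- Centre = (p + z²/2n)/(1 + z²/n) = (0.95 + 0.0031)/1.0062 = 0.9472.
- Half-width = z·√(p(1−p)/n + z²/4n²)/(1 + z²/n) = 0.0173.
- Interval 92.99–96.46%, width 3.47 points. This matches the tabulated 93.0–96.5 and 3.5. Half-width: 3.47/2 ≈ 1.7 points.

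**Size of a difference**

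The documents give no count of discordant patients. Assume a SAP-rule rate of 589/620 = 95.0%, and that 0.5–2% of 620 were below 50 in the window but at 50 or above at the last value: 0.005 × 620 = 3.1 and 0.02 × 620 = 12.4, so 3–12 patients.

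| Late failures | Protocol-rule rate | 95% Wilson CI |
|---|---|---|
| 0 | 589/620 = 95.00% | 92.99–96.46 |
| 3 | 586/620 = 94.52% | 92.43–96.05 |
| 6 | 583/620 = 94.03% | 91.88–95.64 |
| 12 | 577/620 = 93.06% | 90.79–94.81 |

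About 11 such patients (11/620 = 1.8 points) would move the estimate by the planned half-width. In a subgroup of 62, which the plan treats as precise enough, one patient is 1/62 = 1.6 points.

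Changes in the other direction offset these. With a late failures and b patients who are positive in the window and negative later, the protocol rate is (589 − a + b)/620. If a = b = 3, the rate stays at 95.0% although six patients change status. A second rate alone would hide this; a cross-tabulation would not.

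**The case against.** The case for the SAP is good, and most of it stands. The protocol gives the SAP authority over HCV RNA windows, and the SAP states the upper limit and a reason for it. The protocol's own 12-week laboratory window (Table 4) also ends at day 126. The protocol further lists, as a secondary variable, relapse or reinfection that follows an SVR12 and occurs by week 48. That sits badly with a rule under which a later positive value cancels the SVR12; a bounded window removes the conflict. Replacement is not total either, because later values still decide when the window is empty.

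Late failure is also partly reported. Relapse in the SVR24 window and after it approximates the patients who would move from success to failure. But relapse rates are confined to treatment completers with end-of-treatment response and adequate follow-up, and SVR24 and SVR48 are reported in their own follow-up populations. None of these reproduces the rate in the whole core population under the protocol rule.

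Three stronger readings are tempting, and the documents do not support them.

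- **The limit was chosen after results were seen.** The SAP describes interim response analyses as done ("A fourth IA was performed in August 2017"; also October 2016 and January/March 2017). It does not show when the limit was first written, and an earlier SAP may already have contained it. The study is descriptive, with no test or success threshold.
- **The SAP rule can only keep or raise the rate.** A positive in-window value followed by a later negative one lowers it.
- **CPSFU12 mixes two definitions because it accepts any value from day 70.** Backward imputation gives a patient tested only after day 126 an SVR12 result, so the open-ended population matches the endpoint.

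**Conclusion.** The point holds as a gap in reporting. The SVR12 rule differs between the documents, the loss of the last-value rule is not disclosed, and no planned output shows the protocol-defined rate in the core population. It is not an argument against the 70–126 day window, and no data-driven change is claimed.

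The effect on the rate is unknown. The fall from 95.0% to between 94.5% and 93.1% rests on the assumed 0.5–2% late failures, on those patients having HCV RNA measured after day 126, on 620 evaluable patients, and on no offsetting changes. The 1.7-point half-width is only a yardstick, since both rates come from the same patients. The matter is minor and cheap to settle.

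**What to change.** 1. Keep the 70–126 day window as the primary definition, and say in SAP 4.1.1 that it also replaces the protocol's last-value rule.
2. Add SVR12 by the protocol rule (last value from day 70 onward) in the core population as a named sensitivity analysis. Apply the SAP 4.2.3 rule on new HCV treatment: discard values from its start and count those patients as failures. Otherwise relapsers who were successfully retreated would appear as responders.
3. Cross-tabulate success and failure under the two rules, so that changes in each direction are visible.
4. State which value counts when several fall within days 70–126.

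The cost is one extra row in the response table, one small cross-tabulation and a few sentences of text. No new data are needed.
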